NCT03309956

Protocol: AAAR5436

Principal Investigator: [name]

Title: Comparison of Holter with Leadless Patch Ambulatory Electrocardiographic Monitoring in Children

Version Date (Last IRB Approved): 9/26/2018

Study Purpose and Rationale:

The utility of ambulatory electrocardiography has been reported using a variety of devices, including the short-term (24- to 48-hour) Holter monitor and the longer term event monitor (7-30 days). Each monitoring modality has its strengths and limitations. The Holter monitor can detect asymptomatic arrhythmias by continuously recording, however the multiple leads are cumbersome and it is not ideal for capturing infrequent arrhythmias because of the short wear time. The Holter monitor's ability to detect an arrhythmia, or diagnostic yield, was 10% in a retrospective study of 1319 children. The event monitor is preferred for infrequent arrhythmias, however it requires cognitive capacity to press a trigger button, and patient compliance may be difficult in the pediatric population. The adhesive patch monitor (Zio Patch; iRhythm Technologies, San Francisco, California) is a single-lead, intermediate-duration, water-resistant adhesive patch monitoring device that can continuously record for up to 14 days. The Zio patch has demonstrated great utility in the adult population as it detected more arrhythmias in the first 24 hours as compared with the Holter monitor when worn simultaneously. In a retrospective study of 3,209 pediatric patients across the United States who used the Zio patch, the diagnostic yield was 12%. While both the Holter and the Zio patch are continuously recording and are able to detect asymptomatic arrhythmias, to date there has been no direct comparisons of the diagnostic yield (ability to detect an arrhythmia) of the Holter monitor versus the Zio patch in the pediatric population.

Study Design:

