Descriptive statistics will be used for patient demographics and survey results. To compare presence or absence of any of the clinically significant arrhythmias (SVT > 4 beats, VT > 4 beats, advanced second degree or complete AV block, atrial fibrillation or flutter, pause > 2 seconds, PVCs > 5%) over 48 hours, McNemar's test will be used. Further subgroup analysis of each of the arrhythmia types can be done between the 2 devices using McNemar's test again. Logistic regression will be used to determine if age, weight, gender, presence of congenital heart disease, or prior cardiac surgery has an effect on diagnostic yield of Holter monitor versus the Zio patch. Using a power of 80% and allowing for 25% variability, the number of patients needed for the study was determined to be 255 using McNemar's test. We anticipate enrolling about 260 patients in this study.

Study Procedures:

Informed consent will be obtained in a private room in the pediatric cardiology clinic. If the patient agrees to participate in the research, the Holter monitor and the Zio patch will be placed on the patient in that private room. The Holter monitor will be returned to the clinic and the Zio patch will be returned in the mail, per protocol from the manufacturers. The results of both ambulatory ECG monitors will become part of the patient's confidential medical record.

After the data is collected, it will be de-identified and stored in a password protected electronic database on an encrypted endpoint (desktop and laptop computer). The patient satisfaction survey will be a hardcopy that will be stored in a binder locked inside the filing cabinet of the study coordinator. Only research investigators will have access to the electronic database or the binder of patient satisfaction surveys.

Study Devices:

Device name: Holter

Device description: Traditional ambulatory electrocardiographic monitor

Device Model/Version #: H3+ Digital Holter Recorder

Already approved by FDA and used as gold standard

Device name: Zio Patch

Device description: Leadless ambulatory patch electrocardiographic monitor

Device Model/Version #: Zio XT

FDA approved in adults, off-label use in children. This is a Nonsignificant Risk device (21 CFR 812.2(b)); no more than Minimal Risk (45 CFR 46.404/21 CFR 50.51; i.e., 'Section 404').

Research Question(s)/Hypothesis(es):

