Primary objective: This prospective study aims to compare the diagnostic yield (ability to detect an arrhythmia) of the Holter monitor versus the Zio patch in children by having patients wear both devices simultaneously for 48 hours. We will compare the incidence of specific abnormal heart rhythms in children using each device, specifically supraventricular tachycardia 4 beats (SVT), ventricular tachycardia 4 beats (VT), advanced second degree or complete heart block, atrial flutter or fibrillation (AF), pause > 3 seconds, premature ventricular contractions (PVCs) > 5%, premature atrial contractions (PACs) > 5%, and presence of preexcitation suggestive of Wolf Parkinson White syndrome (WPW).

Secondary objective: We will compare the minimum, maximum, and average heart rates, as well as the percent analyzable data for each device over the 48 hours. Tertiary objective: To determine if age, weight, gender, presence of congenital heart disease, or prior cardiac surgery had an effect on diagnostic yield of Holter monitor versus the Zio patch. Quaternary objective: To compare the patient and/or parental satisfaction for the Holter monitor versus the Zio patch using a one page survey at the end of the 48 hour study. Hypotheses: 1. There will be no difference in the diagnostic yield or the heart rate parameters (maximum, minimum, or average heart rate, percent analyzable data) of the Zio patch compared to the Holter monitor during the 48 hours of monitoring. 2. Age, weight, gender, presence of congenital heart disease, or prior cardiac surgery will not affect diagnostic yield of the Holter versus the Zio patch. 3. Patients will prefer the Zio patch over the Holter monitor based on the patient satisfaction survey.

Scientific Abstract:

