Ambulatory electrocardiographic (ECG) monitoring is common diagnostic tool used to detect arrhythmias in the outpatient setting. The traditional Holter monitor is the gold standard ambulatory ECG monitoring device that is commonly used in children. However, it has multiple leads and can be cumbersome. The Zio patch is a new single lead patch ECG monitor that has been FDA approved for use in adults and has been used off-label in children for several years. While both the Holter and the Zio patch are continuously recording and are able to detect asymptomatic arrhythmias, to date there has been no direct comparisons of the diagnostic yield (ability to detect an arrhythmia) of the Holter

monitor versus the Zio patch in the pediatric population. This prospective study aims to compare the diagnostic yield, heart rate parameters, and patient satisfaction of the Holter versus the Zio patch in pediatrics. Patients less than or equal to 21 years of age referred for ambulatory ECG monitoring at the pediatric cardiology clinic at Children's Hospital of New York (CHONY) will simultaneously wear both the Holter and the Zio for 48 hours. Data parameters will be compared using descriptive statistics, McNemar's test, and logistic regression.

Subject Population Justification:

Any patient from birth through 21 years of age who is referred for ambulatory ECG monitoring at CHONY will be recruited for participation in this study. In a large retrospective study using the Zio patch, neonates (under 1 month of age) have used the Zio patch off label, therefore this study will prospectively study the device in all ages from birth through 21 years. We will obtain informed consent in English or in Spanish. Target enrollment is 260 participants.

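### Hypothesis 1 expects no difference in yield, but the plan has no margin and no confidence interval, so a non-significant McNemar test could not support it

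*Combined protocol and SAP*

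**What the plan says.** Under Research Question(s)/Hypothesis(es), hypothesis 1 reads in part: "There will be no difference in the diagnostic yield". It goes on to the heart rate parameters and gives no margin or tolerance for any of them.

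Statistical Procedures assigns McNemar's test "To compare presence or absence of any of the clinically significant arrhythmias" over 48 hours, and allows the same test for each arrhythmia type. The Scientific Abstract repeats this. Logistic regression is kept for covariate effects. In Statistical Procedures, descriptive statistics are for demographics and the survey. The Lay Abstract is looser ("Data parameters will be compared using descriptive statistics", followed by McNemar's test and logistic regression) but adds no method. No section plans a confidence interval for the difference in yield, or an equivalence or non-inferiority test.

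The sample size rests on one sentence in Statistical Procedures: "Using a power of 80% and allowing for 25% variability, the number of patients needed for the study was determined to be 255", by McNemar's test. Planned enrolment is about 260.

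**The concern.** McNemar's test can reject equal yield. Failing to reject it says only that the data did not show a difference. If the investigators' expectation is right, the likely result is a non-significant test, and the plan contains nothing that says how large a difference would still be possible.

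A stated power of 80% might have filled that gap had it been tied to a difference, an alpha and a discordant proportion. It is not, so a non-significant p-value beside 80% power could be read as equal yield when the data do not exclude a material difference. The result may carry weight, because Study Purpose and Rationale says of children that "to date there has been no direct comparisons of the diagnostic yield".

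**Working it through.** **1. Can 255 be reproduced?** Stated inputs (Statistical Procedures): power 80%, 25% variability, McNemar's test. Not stated: alpha, sidedness, test version, difference d. Discordant proportion pd: not clearly stated. The usual paired formula is

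n = [z_alpha × √pd + z_beta × √(pd − d²)]² / d².

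If 25% is taken as pd, with an assumed two-sided alpha of 0.05, then d = 0.0873 gives

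[1.96 × 0.5 + 0.8416 × √(0.25 − 0.00762)]² / 0.00762 = 1.944 / 0.00762 ≈ 255.

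So 255 would correspond to a difference of about 8.7 points, or about 7.8 points one-sided. Neither is stated. Other unstated inputs also land nearby: 12% v 15% with 3% discordance gives 260, and a discordant odds ratio of 3 with 12.5% discordance gives 249. The figure therefore identifies no single design. It cannot be reproduced, but it is not refuted either.

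**2. What a non-significant result could leave open.** Assumed example: 255 pairs, 26 discordant (10.2%), split b = 17 and c = 9.

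- Exact McNemar p = 0.169. Uncorrected chi-square = (17 − 9)²/26 = 64/26 = 2.46, p = 0.117.
- Difference = 8/255 = 3.14 points.
- Standard error = √(26 − 64/255)/255 = 1.99 points.
- Wald 95% interval: 3.14 ± 1.96 × 1.99 = -0.76 to 7.04 points. The paired score interval runs from about -0.8 to 7.4.

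The Holter yield cited in Study Purpose and Rationale "was 10% in a retrospective study of 1319 children". Against that, an upper limit of 7 points or more is not a finding of no difference.

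**3. What 255 pairs can resolve.** Assumed two-sided alpha 0.05; discordances of 5%, 10% and 25% are also assumed. Power was enumerated with M ~ Bin(255, pd) and b given M ~ Bin(M, (pd + d)/(2pd)), rejecting when (2b − M)²/M > 3.84. The half-width is 1.96 × √(pd/255), which is the Wald value at an observed difference of zero.

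| Assumed discordance | Difference with 80% power, uncorrected test | Same, exact test | 95% half-width (Wald, zero difference) |
|---|---|---|---|
| 5% | 3.7 points | 4.0 | 2.7 |
| 10% | 5.3 | 5.7 | 3.9 |
| 25% | 8.6 | 9.0 | 6.1 |

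The 8.6 differs slightly from the 8.7 in step 1 because step 1 uses a normal approximation. A score interval is a little wider: 4.1 rather than 3.9 points for a 13 v 13 split.

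**4. The interval must match the test.** With 14 v 5 discordant pairs among 255 (assumed), the exact test gives p = 0.064, while the Wald interval is 0.2 to 6.9 points and excludes zero. The uncorrected statistic is (14 − 5)²/19 = 81/19 = 4.26, above 3.84. At a difference of zero the paired score interval uses this same statistic, so it and the uncorrected test always agree on significance.

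**The case against.** The strongest reply is that the documents never promise the misuse. The primary objective is only to compare yield. No section says that a non-significant test will be taken as equality, and none claims equivalence or non-inferiority. Hypothesis 1 might be just the statistical null. The paired two-by-two table behind McNemar's test would also allow an interval at the reporting stage without any change to conduct.

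Part of this stands: the harm is a risk in interpretation, not a stated intention. But hypothesis 3 is a directional expectation, so the list reads as predictions and not as formal nulls. Even read as a null, hypothesis 1 needs an interval before a non-significant result can be interpreted, and nothing commits the investigators to report one.

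A second reply is that the 25% may be the discordant proportion, since it stands in the same sentence as McNemar's test. That is possible, so a reader should not infer that discordance is absent from the calculation. It is unclear. On that reading alpha and the difference are still missing.

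A third reply is that an interval alone leaves hypothesis 1 beyond the reach of any planned result. That is right, and it is why the hypothesis itself needs rewording or a margin.

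**Conclusion.** The point holds as a gap between hypothesis and analysis: the outcome that hypothesis 1 predicts is one that the planned test cannot establish. On the assumptions in the table, 255 evaluable pairs would leave differences of roughly 3 to 6 points either way unexcluded, even at an observed difference of zero. Which end applies depends on discordance, which the documents do not clearly give.

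Stronger readings are not supported:

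- A reader might infer that 255 is miscalculated. Missing inputs make it irreproducible and do not show an error.
- A reader might infer that the trial is underpowered for the gap between the cited yields of 12% (patch) and 10% (Holter). Those come from separate retrospective cohorts and are not a design target. The 12% is not said to be a 48-hour yield, and the patch "can continuously record for up to 14 days".
- A reader might infer that the investigators plan to claim equivalence. No section says so.

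The undefined 25% and the missing alpha and difference are, on their own, missing detail. What changes the trial's conclusion is reporting the interval. This should be fixed, though it does not affect the design, the sample size or the data collected.

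**What to change.** Keep 260 patients and McNemar's test.

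1. Add to Statistical Procedures: *The primary result is the paired difference in yield (Zio minus Holter) with a 95% score confidence interval for paired proportions, reported beside the uncorrected McNemar test, with which it agrees. A non-significant test will not be taken as equal yield.*
2. Unless the investigators pre-state a margin, reword the yield part of hypothesis 1 as an estimation aim, for example: *We expect the difference in yield to be small and will report it with its 95% confidence interval.*
3. Secondarily, define the 25% and give the alpha, difference and discordance behind 255 if they are on file. If they are not, add a statement labelled as sensitivity and not as the basis for 255: *With 255 evaluable pairs and an assumed two-sided alpha of 0.05, the uncorrected McNemar test has 80% power for differences of about 3.7, 5.3 and 8.6 points at assumed discordances of 5%, 10% and 25%. The approximate (Wald) 95% half-width at an observed difference of zero is 2.7, 3.9 and 6.1 points, slightly wider with a score interval.*

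Before the result is computed, the yield definition must be reconciled. Study Design and the research question use a pause over 3 seconds and include premature atrial contractions over 5% and preexcitation. Statistical Procedures and the Scientific Abstract use a pause over 2 seconds and omit both.

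The cost is a few sentences and one more reported interval, with no extra patients, visits or data. The downside is a more qualified statement of power.

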Ambulatory electrocardiographic (ECG) monitoring is common diagnostic tool used to detect arrhythmias in the outpatient setting. The traditional Holter monitor is the gold standard ambulatory ECG monitoring device that is commonly used in children. However, it has multiple leads and can be cumbersome. The Zio patch is a new single-lead patch ECG monitor that has been FDA approved for use in adults and has been used off-label in children for several years. While both the Holter and the Zio patch are continuously recording and are able to detect asymptomatic arrhythmias, to date there has been no direct comparisons of the diagnostic yield (ability to detect an arrhythmia) of the Holter monitor versus the Zio patch in the pediatric population. This prospective study aims to compare the diagnostic yield, heart rate parameters, and patient satisfaction of the Holter versus the Zio patch in pediatrics. Patients less than or equal to 21 years of age referred for ambulatory ECG monitoring at the pediatric cardiology clinic at Children's Hospital of New York (CHONY) will be recruited to participate in the study. ECG technicians will obtain informed consent and place the Holter monitor and Zio patch simultaneously on the patient. After 48 hours of monitoring, the patient will mail the Zio patch to the manufacturer and the return the Holter monitor to the clinic. The patient satisfaction survey will be submitted to the researchers in clinic upon completion of the study. Descriptive statistics will be used for patient demographics and survey results. To compare presence or absence of any of the clinically significant arrhythmias (supraventricular tachycardia (SVT) > 4 beats, ventricular tachycardia (VT) > 4 beats, advanced second degree or complete atrioventricular block, atrial fibrillation or flutter, pause > 2 seconds, premature ventricular contractions (PVCs) > 5%) over 48 hours, McNemar's test will be used. Further subgroup analysis of each of the arrhythmia types will be done using McNemar's test again. Logistic regression will be used to determine if age, weight, gender, presence of congenital heart disease, or prior cardiac surgery has an effect on diagnostic yield of Holter monitor versus the Zio patch.

Lay Abstract:

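### Hypothesis 1 predicts no difference in diagnostic yield, but McNemar's test without an interval for the paired difference cannot support that prediction

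*Combined protocol and SAP*

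**What the plan says.** In Research Question(s)/Hypothesis(es), the primary objective is to "compare the diagnostic yield (ability to detect an arrhythmia) of the Holter monitor versus the Zio patch in children". Hypothesis 1 in the same section then predicts the result: "There will be no difference in the diagnostic yield or the heart rate parameters".

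Statistical Procedures names the analysis. For presence or absence of any clinically significant arrhythmia "over 48 hours, McNemar's test will be used". The Scientific Abstract adds: "Further subgroup analysis of each of the arrhythmia types will be done using McNemar's test again". The sample size uses the same test: "the number of patients needed for the study was determined to be 255 using McNemar's test". Logistic regression is planned for the effect of patient factors on yield, which is the subject of Hypothesis 2.

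On description, Statistical Procedures says: "Descriptive statistics will be used for patient demographics and survey results". The Lay Abstract is broader: "Data parameters will be compared using descriptive statistics, McNemar's test, and logistic regression".

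No section gives a confidence interval, an equivalence or non-inferiority margin, or a rule for interpreting p > 0.05.

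**The concern.** The null hypothesis of McNemar's test is that the two devices have equal yield. A significant result is valid evidence against Hypothesis 1. A non-significant result means only that a difference was not shown. It may reflect close agreement, or data too imprecise to tell. The prediction can therefore be refuted under the plan but not supported.

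The documents describe the Holter as the gold standard, the patch as off-label in children, and a direct paediatric comparison as lacking. A finding of no significant difference could then be taken to mean that the devices are interchangeable, while the data still allow a sizeable gap in detection in either direction. An interval for the paired difference would show how large a gap remains possible.

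**Working it through.** **The plan's own figure.** The 255 pairs cannot be reproduced uniquely, because alpha, sidedness, the difference to detect and the discordant proportion are not stated, and the 25% variability is not defined. The usual formula is n = [z(1−α/2)·√ψ + z(power)·√(ψ − d²)]² / d², with ψ the discordant proportion and d the difference in yield. If the 25% is read as ψ, with two-sided α = 0.05 and 80% power, n = 255 corresponds to d = 0.0873: (1.96 × 0.5 + 0.842 × 0.492)² / 0.0873² ≈ 255. That is only one possible reading. Whichever is right, the number is sized to detect a difference. The point below uses 255 only as the number of pairs.

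**Inputs.** N = 255 (Statistical Procedures). Background Holter "diagnostic yield, was 10% in a retrospective study of 1319 children" (Study Purpose and Rationale). The discordant counts are assumed for illustration. Let b = Zio-only detections, c = Holter-only detections, and δ = Zio minus Holter.

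**Step 1: McNemar's test.** The statistic is (b − c)²/(b + c).
- 4 v 4: 0/8 = 0, p = 1.00.
- 25 v 25: 0/50 = 0, p = 1.00.

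The exact version also gives p = 1.00 for both.

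**Step 2: Tango 95% interval.** The limits are the values of δ at which |b − c − Nδ| / √{N[2q + δ(1 − δ)]} = 1.96. Here q = [√(B² − 4AC) − B]/(2A), with A = 2N, B = −(b + c) + (2N − b + c)δ and C = −cδ(1 − δ).
- 4 v 4, at δ = 0.0261: q = 0.00985. Numerator 255 × 0.0261 = 6.64; denominator √11.49 = 3.39; ratio 1.96. Interval **−2.6 to +2.6 points**.
- 25 v 25, at δ = 0.0556: q = 0.0762. Numerator 255 × 0.0556 = 14.17; denominator √52.26 = 7.23; ratio 1.96. Interval **−5.6 to +5.6 points**.

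Against a 10% yield, 5.6 points is 56%, and 2.6 points is 26%. The p-values are identical, so they carry none of this information.

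**Step 3: how far this depends on the counts.** The two tables have discordance of 8/255 = 3.1% and 50/255 = 19.6%. With no observed difference, the simple large-sample half-width is 1.96·√(ψ/255).

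| Assumed discordance | 95% half-width (points) |
|---|---|
| 5% | 2.7 |
| 10% | 3.9 |
| 19.6% | 5.4 |

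At the background yields of 10% (Holter) and 12% (Zio), two unrelated devices would disagree in 0.10 × 0.88 + 0.12 × 0.90 = 19.6% of patients. The 25 v 25 table is therefore an extreme case for devices worn together, unless yields in this clinic are well above background. At lower discordance the interval is narrower. The documents do not say what discordance to expect, and the p-value would not reveal it.

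**Step 4: whether another planned analysis supplies the interval.** The logistic regression concerns patient factors, not the overall device difference. Describing the yield of each device separately would not give the uncertainty of a paired difference, which depends on the discordant pairs.

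**The case against.** The primary objective is only to compare the devices, and no section claims equivalence or non-inferiority. Hypotheses 1 and 2 are both worded as nulls, so Hypothesis 1 may be a conventional null statement. This has force. However, Hypothesis 3 in the same list is a directional prediction, and on either reading failure to reject a null does not establish it.

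A reader might infer more than the documents support:

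- *That the sponsor will report p > 0.05 as proof of no difference.* Nothing says so. The gap is that no rule rules it out.
- *That the plan reports p-values alone.* Statistical Procedures and the Scientific Abstract assign descriptive statistics to demographics and the survey, but do not say they are confined to these. The Lay Abstract can be read as allowing yield to be described by device. What is absent is an interval for the paired difference.
- *That the patch is expected to lose yield.* The background figures point the other way (12% for Zio, 10% for Holter, from separate retrospective studies). The concern is uncertainty in both directions.
- *That this shows 255 to be wrong, or McNemar's test unsuitable.* The sample size is under-specified rather than shown to be wrong, and McNemar's test is a proper test for a paired difference.

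It is also true that an interval can be computed later from the same 2×2 table, so no information is lost. Naming it now fixes what the conclusion will rest on before the results are seen.

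**Conclusion.** The point holds as a gap in the planned inference: the analysis can contradict the yield part of Hypothesis 1 but cannot support it. That conclusion follows from the text and needs no assumed numbers.

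The size does rest on assumptions. At 255 pairs and p = 1.00, the 95% interval could be ±2.6 points (4 v 4) or ±5.6 points (25 v 25). These counts are not protocol figures, the second table is extreme at background yields, and the 10% reference yield comes from a separate retrospective study. The design and the data to be collected are unaffected. This should be fixed, but it does not invalidate the trial.

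The point covers diagnostic yield only, not the heart rate parameters or percent analyzable data named in the same hypothesis.

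**What to change.** 1. Alongside McNemar's test, report the paired difference in yield (Zio minus Holter) with a 95% CI for paired proportions (Tango or Newcombe), and base the conclusion on yield on that interval.
2. State that p > 0.05 alone is not evidence of no difference.
3. Reword the yield part of Hypothesis 1 as a comparison.
4. Apply the interval to one arrhythmia composite. Study Design and Research Question(s)/Hypothesis(es) list pauses over 3 seconds and include PACs and preexcitation. Statistical Procedures and the Scientific Abstract list pauses over 2 seconds and include neither. These lists must be reconciled first.
5. Only if a formal claim of no difference is wanted: justify a two-sided margin, and fix it and the CI level before results are compared.

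Items 1 to 3 cost a few lines of text and analysis code, with no new data and no extra patients. The downside is that the conclusion may be less favourable than a statement of no significant difference. Item 5 costs more, since it also needs a check of what 255 pairs can deliver for the chosen margin.
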